Phases 5 and 6. These phases will involve assessments of anthropometric variables (weight, height), lifestyle variables (e.g., physical activity, alcohol consumption, smoking, etc.), and psychological variables of interest in both the experimental and control groups at 1- and 3-month follow-ups.

OUTCOMES

All outcomes will be assessed at baseline (T0), post-intervention (T1), and at 1 (T2) and 3 months (T3) follow-ups.

Date: 21/11/2023 Version number: 4.0

Primary Outcome:

• Weight loss, measured in kilograms and expressed in percentage of weight loss in both the experimental and control groups, assessed in terms of change over time and in reference to the intervention condition. A reduction of at least 3% compared to the baseline assessment is expected at T1, with a maintenance of this weight loss at T2 and T3 and with a higher incidence of weight loss in the experimental group compared to the control group. The choice of this criterion has been based on retrospective audits conducted in the same Hospital Unit.

Secondary Outcomes:

- Increase in healthy and sustainable dietary behaviors measured through the Sustainable and Healthy Dietary Behaviors Scale (SHDB; Kawasaki et al., 2022).
- Balancing of psychological well-being levels measured through the Psychological Well-Being Scales-42 (PWBs; Ryff & Keys, 1995; Ruini et al., 2003).
- Promotion of functional eating styles assessed through the Dutch Eating Behavior Questionnaire (DEBQ; Van Strien et al., 1986; Dakanalis et al., 2013).
- Reduction of psychological distress levels measured through the Depression and Anxiety Stress Scale-21 (DASS-21; Lovibond & Lovibond, 1995; Bottesi et al., 2015).
- Reduction in the use of dysfunctional cognitive justifying mechanisms related to food intake evaluated through an adapted assessment index from Plazonic & Herrada (2020).

Participants

Inclusion Criteria. Patients will be eligible for inclusion in the study if they: a) are affiliated with the Clinical Nutrition and Metabolism Unit of Policlinico S. Orsola-Malpighi; b) have a BMI \geq 30; c) are aged \geq 18 years; d) voluntarily agree to participate in the study; e) have access to a computer and can use it independently.

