- Psychological Well-Being Scales 42 items (PWB; Ryff, 1989) to evaluate psychological well-being through 42 items with a six-point Likert scale response, divided into six dimensions: autonomy, environmental mastery, personal growth, positive relations with others, purpose in life, and self-acceptance. The Italian version by Ruini and colleagues (2003) will be used for this study.
- Dutch Eating Behavior Questionnaire (DEBQ; Van Strien et al., 1986) to assess dysfunctional eating styles through 33 items with a five-point Likert scale response, divided into three subscales: dietary restraint, external eating, and emotional eating. For this research, only 21 items selected based on their saturation level will be used. The Italian version by Dakanalis and collegues (2013) will be used for this study.
- Depression and Anxiety Stress Scale-21 (DASS-21; Lovibond & Lovibond, 1995) to assess
 levels of psychological distress through 21 items with a 4-point Likert scale response, divided
 into three sub-scales: anxiety, depression, and stress. The Italian version by Bottesi and
 colleagues (2015) will be used for this study.

Date: 21/11/2023 Version number: 4.0

• Dysfunctional cognitive justification mechanisms use (adapted from Taylor & Sheeran, 2014; Plazonic & Herrada, 2020). To evaluate dysfunctional cognitive justification mechanisms, an ad-hoc assessment index will be administered. This index presents three hypothetical scenarios (related to emotional distress, social context, and habitual behavior) that could pose dilemmas for participants regarding adherence to a healthy diet. For each scenario, participants will be asked to indicate their level of identification with it on a 10-point Likert scale and to specify the types of cognitive justification mechanisms most frequently used. Participants will choose from six possible responses to justify their food choices: availability (e.g., it's right in front of me), compensatory behavior (e.g., I'll compensate for what I ate with physical activity), exception to the rule (e.g., I never do it, so I can do it now), deservingness (e.g., today has been a very difficult day, I deserve to eat something good), curiosity (e.g., I saw the advertisement for this product, and it seemed very enticing), irresistibility (e.g., I can't resist the temptation to eat this food). The index has been translated in Italian by the researchers involved in this study.

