Statistical Package for Social Science 29.0 (SPSS) will be used for data analysis. Descriptive statistical analyses (frequencies, means, medians, modes, and standard deviations) will be conducted to analyze the sociodemographic, anthropometric, clinical characteristics, and lifestyle of the sample, as well as the mean scores on administered questionnaires. To assess differences between the experimental and control groups at post-intervention and the 1- and 3-month follow-ups in terms of weight loss, healthy and sustainable dietary behaviors, and optimal psychological functioning (psychological well-being, eating styles, psychological distress, and use of justification mechanisms), repeated measures analysis of variance (ANOVA) will be performed, using time (T0, T1, T2, T3) as a within-subject factor and group (E or C) as a between-subjects factor. Missing data will be handled through Intention to Treat (ITT) Analysis. Differences will be considered significant at $p \le 0.05$.

ETHICAL PROCEDURES

The procedures regarding the conduction, execution, and data collection of this research adhere to the ethical principles outlined in the Declaration of Helsinki and its revisions. The study will be conducted in accordance with regulatory requirements and legal obligations (DM 17/12/2004).

During the screening phase, eligible subjects will receive all relevant information on the study, both in written and oral form. Additionally, before proceeding with data collection, informed consent and consent for the processing of personal data will be obtained for each participant, in an anonymous and aggregated form, in accordance with Law 675/1996 and Law 196/03 on the protection of individuals and the processing of personal data.

A copy of the informational and consent forms for participation in the research and data processing will be presented by the referring physician to the potential participant deemed eligible for the study. If interested, the participant will sign the consent forms, which will be collected and stored in a designated

Date: 21/11/2023 Version number: 4.0

space at the Department while informational forms will be left to the participant.

The data collected will be digitized anonymously using statistical software for data processing (SPSS).

Furthermore, a decoding list of the code assigned to each individual participant will be securely stored

in encrypted form exclusively at the Department of Psychology of the University of Bologna.

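### As described, the justification-mechanism index has no response for not justifying and no stated score, so it does not directly measure the reduction in use that the ANOVA is meant to test

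*Combined protocol and SAP*

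**What the plan says.** The Secondary Outcomes list includes "Reduction in the use of dysfunctional cognitive justifying mechanisms related to food intake evaluated through an adapted assessment index". The Hypotheses section expects the experimental intervention to do better than the control on this. Under Study Design, Phase 3, the psychological sessions teach patients to notice such justifications and put more functional thoughts in their place.

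Under Methods of Assessment, Phase 2, "an ad-hoc assessment index will be administered". It has three scenarios: emotional distress, social context and habit. Each scenario has two parts. The first is a rating, in which "participants will be asked to indicate their level of identification with it on a 10-point Likert scale". The other part of the item asks patients "to specify the types of cognitive justification mechanisms most frequently used". For the second part, "Participants will choose from six possible responses to justify their food choices": availability, compensation, exception, deservingness, curiosity and irresistibility. The same index is given at T0, T1, T2 and T3.

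The Statistical Analysis section closes its list of outcomes with "and use of justification mechanisms), repeated measures analysis of variance (ANOVA) will be performed", using time (four levels) and group (two levels) as factors. It does not say which variable from the index is analysed. No section gives a score, states whether one or several responses may be chosen, or states whether an answer is compulsory.

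**The concern.** The hypothesis is about amount: patients should justify less. The mechanism item is about kind: which justifications a patient uses most. The intended end state, a patient who meets the scenario and no longer justifies eating, has no response among those described.

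Two things are at stake. First, a stated target of the intervention may be assessed with a variable that moves little, or not at all, when the target is reached. Second, with no score defined, at least three variables could later be called use (the chosen type, a count of types, the identification rating), and the choice could be made after the data are seen. A gap in the baseline form is also hard to repair, because T0 cannot be collected again.

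**Working it through.** The plan states no figure for this index, so there is none to reproduce. The sample-size calculation (36 before dropout, about 50 recruited) is not specific to it. The check is what score each reading of the text allows.

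**Inputs.** Three scenarios, six responses and a 10-point rating per scenario (Methods of Assessment, Phase 2); four time points and two groups (Statistical Analysis).

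| Reading | Score | Attainable range | Can it show less use? |
|---|---|---|---|
| A. One response required per scenario | scenarios with a mechanism | 3 × 1 = 3, always | No; variance 0 |
| B. Several allowed, at least one required | types ticked over three scenarios | 3 × 1 = 3 to 3 × 6 = 18 | Partly; floor at 3 |
| C. One response, with a *none* option | scenarios with a mechanism | 0 to 3 | Yes |
| D. Several allowed, with a *none* option | types ticked | 0 to 18 | Yes, as variety |
| E. Identification rating, assumed coded 1 to 10 | sum of three ratings | 3 × 1 = 3 to 3 × 10 = 30 | Can fall, but is not use |

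Readings A and B are assumptions about how the described form works. C and D need a response that the protocol does not describe.

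**Reading A.** Every patient scores 3 at every visit, so an ANOVA on the count has no variation to analyse. What remains is the type chosen, which is nominal. If the six types were coded 1 to 6, a move from availability to deservingness would change the code by anything from −5 to +5 depending on the numbering, and half of all numberings would show a fall.

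**Reading B, illustration.** Assume each mechanism is endorsed independently with probability q, and that a patient who endorses none must still tick one.

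- Expected total if none is allowed: 3 × 6q.
- Expected total if at least one is required: 3 × [6q + (1 − q)^6].
- At q = 0.30: 3 × 1.8 = 5.40, against 3 × (1.8 + 0.1176) = 5.753.
- At q = 0.05: 3 × 0.3 = 0.90, against 3 × (0.3 + 0.7351) = 3.105.
- Fall: 5.40 − 0.90 = 4.50, against 5.753 − 3.105 = 2.648.
- Ratio: 2.648 / 4.50 = 0.59, so about 41% of the fall is lost to the floor.

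The values of q are illustrative and are not taken from the protocol.

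**What a count under B means.** The item asks for the mechanisms used most often, which is a relative question. A patient who justifies every day and one who does so once a month can tick the same boxes. The count therefore reflects variety of mechanisms, not how often they are used.

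**Reading E.** The rating suits an ANOVA better than the other parts. It records how far the patient identifies with the scenario, however, and a patient may still recognise the scenario after ceasing to justify eating in it.

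**The case against.** A reader might infer that the index forces one choice per scenario, so that the between-arm difference in use is zero by construction and the outcome cannot be answered at all. The documents do not support that. The item refers to types of mechanism in the plural, nothing says only one may be chosen, and nothing says an answer is compulsory. With several choices a count can fall, and if blanks are allowed the floor disappears. A reader might also infer that nominal codes will be averaged; the Statistical Analysis section never says so.

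The form and the scenario texts are not reproduced in the protocol. A *none* response missing from a one-paragraph description may still be on the form, and a scoring rule may exist elsewhere. How closely identification with a scenario tracks giving in to it cannot be judged without the scenario wording. This is also a pilot, and the index serves one secondary outcome.

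These points stand and make the conclusion conditional. They do not remove it. As described, no reading gives a direct measure of how much justification is used: the single choice gives kind, the multiple choice gives variety, and the rating gives identification.

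**Conclusion.** The concern holds in conditional form. The protocol names a reduction in use as a secondary outcome and sends it to a repeated-measures ANOVA. The index it describes has no stated score and no response for the state that the intervention aims at.

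The size depends on an unstated rule. With one required response per scenario, the count is fixed at 3 of 3 and no reduction can be shown. With several allowed and at least one required, the total can fall from as much as 18 to 3; in the illustration above the visible fall is 2.65 rather than 4.50. With blanks allowed the floor goes, but the count still measures variety. The identification rating can fall in any case and is at best indirect.

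It would go too far to say that the outcome cannot be assessed, because forced single choice is not stated. Stating the existing scoring would settle which variable is analysed, but on the items described that variable would still not be frequency of use. This affects one of five secondary outcomes; the primary outcome and the sample size are untouched.

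**What to change.** Before baseline collection:

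- Add a *none of these* response to each scenario, or a short frequency rating for each mechanism.
- State whether one or several responses are allowed and whether an answer is required.
- Define the use score in advance: either the number of scenarios (0 to 3) with a mechanism used, or the mean frequency rating.
- Analyse that score with a method suited to it and adjusted for T0, for example an ordinal or binomial mixed model for the 0 to 3 count.
- Report the identification rating as a separate outcome under its own name, and the type of mechanism by frequencies only.

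The cost is low: an added response or rating in an online form that the team itself adapted and translated, plus a short analysis paragraph. The downsides are slightly less comparability with the source index and, if the change is made during the study, communication to the ethics committee as the Ethical Procedures section requires for relevant modifications.

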participation and data processing. Consent collection will be carried out by one of the researchers

belonging to the clinical research team.

Phase 2. Participants who have provided their informed consent will be assigned to either the

experimental group (E) or the control group (C) using a 1:1 allocation ratio. To ensure a fair distribution

within the groups, a block randomization method will be employed. The allocation sequence will be

generated using a computer.

Phase 3. Participants from both groups will fill-in a self-report online questionnaire through the

Qualtrics platform. This questionnaire will collect socio-demographic (e.g., age, education, occupation,

etc.), anthropometric (weight, height), clinical (e.g., weight history, current weight, medical conditions,

5

Date: 21/11/2023 Version number: 4.0

etc.), and lifestyle data (e.g., physical activity, alcohol consumption, smoking, etc.). Additionally, participants will complete a set of self-administered questionnaires to assess the psychological variables of interest.

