Weight measurement will also be confirmed by the Unit's referring physician during routine patient visits. Participants in the experimental group will participate in 6 weekly group session of two hours each. One part will be held by a trained dietitian and will focus on nutritional education, particularly emphasizing the adoption of healthy and sustainable eating behaviors. Nutritional education will cover topics related to the causes and risk factors of obesity, nutritional principles of foods, preparation of balanced meals, food labels reading, and the importance of physical activity. The remaining part will be dedicated to a group psychological intervention inspired by the principles of Well-Being Therapy (WBT; Fava, 2016a) and will be held by a trained psychologist. This intervention aims to promote weight loss, healthier and more sustainable eating behaviors, and an optimal psychological functioning. During these sessions, participants will be introduced to the six dimensions of psychological well-being: 1) selfacceptance, 2) personal growth, 3) purpose in life, 4) positive relations with others, 5) environmental mastery, and 6) autonomy (Ryff, 1996). Gradually, cognitive-behavioral strategies will be provided to enhance psychological well-being and seek a balance between the presented dimensions through selfmonitoring of well-being episodes, restructuring thoughts that interrupt well-being, and exposure tasks to optimal experiences. Additionally, participants will be given cognitive-behavioral tools to recognize justifying cognitive mechanisms and replace them with more functional cognitions related to eating. These objectives will also be achieved through the use of a food diary to highlight emotions and thoughts experienced during food intake. The control group, on the other hand, will receive treatment as usual (TAU) by participating in 6 two-hour group sessions of Basic Nutritional Intervention (BNI) held by a trained dietitian. This course focuses on promoting healthier lifestyles through nutritional education, diet monitoring using a dedicated food diary, and recommendations for proper physical activity.

Phase 4. A post-intervention assessment will be conducted for anthropometric variables (weight, height), lifestyle variables (e.g., physical activity, alcohol consumption, smoking, etc.), and psychological variables of interest in both the experimental and control groups.

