Exclusion Criteria. Exclusion criteria for this study include: a) lack of the informed consent to participation in the study; b) limited knowledge of the Italian language; c) presence of cognitive deficits; d) meeting the diagnostic criteria for one or more of the following psychiatric diagnoses: binge-eating disorder (BED), drug and/or alcohol abuse, psychotic disorders, neuro-cognitive disorders, suicidal behaviors; e) participation in another weight loss study or program; f) taking weight loss medications; g) engaging in individual or group psychotherapeutic interventions; h) having undergone weight loss surgery in the 16 months preceding the study's commencement and during the entire study period (approximately five months); i) in women, being pregnant or planning pregnancy in the 16 months preceding the study and during the entire study period (approximately five months).

Date: 21/11/2023 Version number: 4.0

METHODS OF ASSESSMENT

Phase 1 – Screening

An initial screening assessment based on inclusion and exclusion criteria will be conducted by a physician and the multidisciplinary staff of the Unit.

Phase 2 – Baseline Assessment

All subjects included in the study will be asked to complete the following self-administered questionnaires online:

- Ad-hoc form for socio-demographic, anthropometric, clinical, and lifestyle data collection: includes socio-demographic information (e.g., age, education, occupation), anthropometric data (weight, height), clinical history (e.g., weight history, current medical information), and lifestyle factors (e.g., physical activity, alcohol use, smoking). Weight measurement will also be confirmed by the Unit's referring doctor.
- Sustainable and Healthy Dietary Behaviors (SHDB; Kawasaki et al., 2022) to assess the implementation of healthy and sustainable dietary behaviors through 30 items with a six-point Likert scale response. Items are divided into five sub-scales: food choices, storing, cooking, food consumption and food disposal. As this questionnaire has not yet been translated and validated in Italian, it has been translated by the researchers involved in this study.

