Phases 4, 5, and 6 – Post-intervention and Follow-up Assessments

At the end of the intervention and at the 1 and 3-month follow-ups, all participants will fill-in the following questionnaires online:

- Ad-hoc form for anthropometric data evaluation for assessing Body Mass Index (BMI) and changes in lifestyle (e.g., physical activity, alcohol consumption, smoking).
- Sustainable and Healthy Dietary Behaviors (SHDB; Kawasaki et al., 2022).
- Psychological Well Being Scales 42 item (PWB; Ryff, 1989; Ruini et al., 2003).
- Dutch Eating Behavior Questionnaire (DEBQ; Van Strien et al., 1986; Dakanalis et al., 2013).
- Depression and Anxiety Stress Scale-21 (DASS-21; Lovibond & Lovibond, 1995; Bottesi et al., 2015).
- Assessment of Justificatory Cognitive Mechanisms (adapted from Taylor & Sheeran, 2014; Plazonic & Herrada, 2020).

Body weight assessment will also be verified by the medical staff during follow-up visits.

CONTEXT

The study will be conducted partly at Policlinico Sant'Orsola-Malpighi, in the Clinical Nutrition and Metabolism Unit of S. Orsola Hospital, and partly online via the Microsoft Teams platform.

Date: 21/11/2023 Version number: 4.0

STATISTICAL CONSIDERATIONS

Sample Size Calculation

The sample size was assessed using G*Power 3.1 statistical software. Based on a previous study conducted in the same recruitment center with the same clinical population (Zhu et al., 2022), the sample size was estimated considering an effect size of 0.25, a type I error < 0.05, and a type II error (power) of 0.95, for 2 groups and 4 measurements (baseline; post-intervention; 1-month follow-up; 3-month follow-up). It is estimated that a sample size of 36 subjects is sufficient. Considering a 30% dropout risk in this clinical population (Brantley et al., 2014), it is estimated to recruit approximately 50 subjects, 25 for the experimental condition and 25 for the control condition.

Statistical Analysis

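### The plan names no source of record for follow-up weight and no rule for using the Unit's weight when the online form is missing, so participants who stop completing forms may lose the primary outcome

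*Combined protocol and SAP*

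**What the plan says.** Under Methods of Assessment, the section on Phases 4, 5 and 6 opens: "At the end of the intervention and at the 1 and 3-month follow-ups, all participants will fill-in the following questionnaires online". The first instrument listed is an "Ad-hoc form for anthropometric data evaluation for assessing Body Mass Index (BMI) and changes in lifestyle". It is followed by the SHDB, PWB, DEBQ, DASS-21 and the justification index. The section closes: "Body weight assessment will also be verified by the medical staff during follow-up visits".

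The Unit has the same secondary role elsewhere. The baseline section says "Weight measurement will also be confirmed by the Unit's referring doctor", and Study Design, Phase 3, says "Weight measurement will also be confirmed by the Unit's referring physician during routine patient visits". Phase 3 describes the baseline mode: "Participants from both groups will fill-in a self-report online questionnaire through the" Qualtrics platform, with weight and height among the items.

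Study Design, Phases 4 to 6, says that weight and height are assessed in both groups but names no mode. Outcomes defines the primary outcome as weight loss, in kilograms and as a percentage, at T0 to T3. Participants, inclusion criterion (a), requires affiliation with the Unit. Sample Size Calculation sets recruitment at about 50, "Considering a 30% dropout risk in this clinical population". Statistical Analysis covers missing data only by reference to intention to treat.

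**The concern.** A measurement that verifies an entry presupposes that there is an entry. Someone who leaves the course and stops answering the online battery makes no entry, and the plan gives no other route by which a weight reaches the analysis. Yet the participants are patients of the Unit, and the protocol refers to visits at which weight is checked. A source that does not depend on the questionnaires therefore exists for at least some of them, and the plan does not use it.

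Two things are at stake. One is precision, because weights that could have been retrieved are lost. The other is bias: if those who leave lose less weight, and if the two courses, which differ in content, lose people at different rates, then a comparison of those with weights is not a comparison of those randomised. A measured weight is better than any statistical substitute for it. The point concerns collecting the outcome after a participant stops, not modelling what is missing.

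**Working it through.** **Which weight is used.** Three questions were put to the text.

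- Which value is analysed if the form and the Unit differ? Not stated.
- May a Unit weight be used when the form is missing? Not stated.
- Are Unit visits scheduled at T1, T2 and T3? Not stated; the text mentions routine visits and follow-up visits without dates.

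**Length of the battery.** From Methods of Assessment: SHDB 30 + PWB 42 + DEBQ 21 (the items selected) + DASS-21 21 = 114 items, before the justification index and the ad-hoc form.

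**The plan's own sample size.** Inputs from Sample Size Calculation: effect size f = 0.25, alpha 0.05, power 0.95, k = 2 groups, m = 4 measurements. Assumed because not stated: correlation between measurements rho = 0.5 and epsilon = 1. For the group-by-time interaction, lambda = f² × N × m / (1 − rho), df1 = (k − 1)(m − 1) and df2 = (N − k)(m − 1).

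- N = 36: lambda = 0.0625 × 36 × 4 / 0.5 = 18, df 3 and 102, power 0.952. N = 34 gives 0.939, so the stated 36 is reproduced.
- Dropout: 36 / 0.70 = 51.4, or 52, against the stated figure of about 50.
- 50 × 0.30 = 15 lost and 50 − 15 = 35 left, one below 36. Power at 35 is 0.946.

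**What Unit weights could recover.** The documents give no recovery figure, so a range is shown. Evaluable = 35 + 15r, and the relative standard error is √(35/n), with n rounded to a whole number of participants. Power is computed at the unrounded count.

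| Share recovered, r (assumed) | Evaluable | n used | SE relative to 35 | Reduction | Power |
|---|---|---|---|---|---|
| 25% | 38.75 | 39 | 0.947 | about 5% | 0.966 |
| 50% | 42.5 | 42 | 0.913 | about 9% | 0.978 |
| 75% | 46.25 | 46 | 0.872 | about 13% | 0.987 |
| 100% | 50 | 50 | 0.837 | about 16% | 0.992 |

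**Single missed forms.** A conventional repeated-measures ANOVA drops anyone who lacks one time point. With independent non-response q at each of three post-baseline visits (assumed), complete cases = 50 × (1 − q)³. For q = 5%, 10%, 15% and 20% this is about 43, 36, 31 and 26, with power about 0.98, 0.95, 0.91 and 0.85.

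**Bias illustration.** Assumed: completers lose 3% in both arms, leavers lose 0%, and dropout is 20% in one arm and 40% in the other (5 + 10 = 15 of 50, or 30% overall).

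- Only those with weights: 3.0% v 3.0%, difference 0.
- All randomised: 0.80 × 3 + 0.20 × 0 = 2.4% and 0.60 × 3 + 0.40 × 0 = 1.8%, difference 0.6 points.
- Same data with baseline carried forward for leavers: 2.4% v 1.8%. In this example the distortion arises only when the analysis is restricted to those with weights.

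**The case against.** The strongest reply is that the protocol nowhere orders a Unit weight to be discarded. Study Design says that weight is assessed in both groups in Phases 4 to 6 without tying it to the form, and a sensible team might simply use the clinic value. This stands in part. A reader might infer that anyone who stops completing forms is certain to lose the primary outcome; the text is silent on this, so only a possible loss can be claimed.

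A reader might also infer that the Unit is still weighing those who leave. That is not established. Criterion (a) requires affiliation, not attendance, and no visit schedule is given. The recoverable share is therefore unknown, and the gain could be small.

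Third, the 30% loss is already allowed for in recruitment. This also stands: 35 evaluable gives power 0.946 against a target of 0.95, so the point does not show an underpowered trial. Recovered weights would mostly be a gain over the planned precision.

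Fourth, the plan invokes intention to treat, and the 0.6-point example assumes an analysis of available weights only. The example is conditional on that, and nothing in the documents shows that leavers lose less weight. But the intention-to-treat sentence names no method and supplies no outcome data, so it does not answer the question of collection.

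**Conclusion.** The concern holds as a gap in how the primary outcome is collected. As written, follow-up anthropometry rests on a participant-completed online form, the Unit's measurement only verifies it, and no source of record or substitution rule is given. With 30% dropout planned, up to about 15 of 50 participants may have no follow-up weight even where the Unit has one.

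The precision at stake is a standard error about 5% to 16% smaller than with 35 evaluable, for recovery of 25% to 100% of those lost; the recovery range is assumed. The bias at stake cannot be sized from the documents. The 0.6-point illustration rests on an assumed 0% loss in leavers, an assumed 20% v 40% split and an analysis confined to those with weights. The power figures rest on rho = 0.5 and epsilon = 1. No stated figure in the plan is shown to be wrong. Because weight is the primary outcome and the change is cheap, it should be made.

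**What to change.** In the section on Phases 4 to 6, and consistently in Study Design and Outcomes:

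- Name the Unit-measured weight as the primary-outcome value.
- State that stopping sessions or forms is not withdrawal from follow-up. Obtain the Unit weight from visit records for every randomised participant who has not withdrawn consent, whether or not sessions or forms were completed.
- Pre-specify non-overlapping windows around T1, T2 and T3. T2 is only one month after T1, so wide windows would meet. Open the T1 window no earlier than the last session, so that a mid-course weight cannot count as post-intervention.
- Use the self-reported weight only as a fallback when no Unit weight exists in the window, and flag it in the data.
- Check that consent covers use of routine weights after stopping (the consent pages were not available for this review). Check also that a linkage procedure exists, since Ethical Procedures keeps the decoding list solely at the Department of Psychology.

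The cost is about one protocol paragraph, possibly a line in the consent form, and extraction from visit records. The downside is that some weights will be off the exact assessment date, and some leavers will have no Unit visit in the window and will still be missing.
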